# 4.4 Sample size calculation

As this is a proof-of-concept (PoC) pilot study, the sample size is aimed at showing the impact of the use of the MMC on patient empowerment and exploring associations, rather than statistically significant relations. Therefore, no formal sample size and power calculation is done. A number of 30 participants per site is the number of subjects that we estimate to be sufficient to investigate the impact of using the medication management centre and associated tools.

To explore potential effectiveness of the tool, results will be compared with those of matched historical controls obtained from the control arm of the U-PGx project. While the study is not aimed at or powered for statistical comparisons, we are in the unique position to have a access to a substantial cohort of comparable patients. Controls will be matched for age, sex and type and number of mediations. These results will help to design a larger study to perform a formal statistical analysis of the effect of the medication management system and associated tools.

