# 2. OBJECTIVES

# 2.1 Primary objective

The primary objective is to assess the impact of the developed medication management centre on the patient empowerment of polypharmacy patients, thereby improving drug safety.

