Effectiveness in the prevention of ADRs and the ability to identify drug-drug-gene interactions will be explored as a secondary endpoint by comparing results of the pilot study with those obtained from matched historical controls obtained from the control arm of the U-PGx project. This control arm is suitable as historical control group for the EmPaSafe study because of its alignment in key aspects, allowing for meaningful comparisons:

- Genotyped but not empowered with PGx Data: Participants in the U-PGx control arm were genotyped retrospectively, meaning their PGx information was available but not actively utilized in their care. This setup provides a unique baseline to assess the effectiveness of the MMC and the empowerment of EmPaSafe patients with PGx data, as we can analyse whether access to their genetic information and medication adjustments reduces ADRs and improves drug efficacy.
- Comparable Follow-up and Monitoring Protocols: The U-PGx control arm and the EmPaSafe study share similar follow-up methods, including regular monitoring for ADRs and the use of similar questionnaires. This similarity minimizes variation in data collection processes, allowing us to more directly compare ADR prevalence and other outcomes between the two groups.
- Matching for Key Variables: The control group will be matched to EmPaSafe participants based on age, sex, and type and number of medications, controlling for these variables in the analysis. This matching enhances the comparability of the two cohorts and strengthens the reliability of conclusions drawn about the impact of empowering patients with PGx data through the MMC.

Using the U-PGx control arm as a historical comparison thus allows EmPaSafe to evaluate the added value of PGx-informed care without needing a concurrent control group, streamlining the study while leveraging pre-existing data to explore the MMC's role in improving medication safety and personalization.

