#### 3.2 Patient journey

The patient journey starts when the patient receives a first prescription for one of the index drugs (see table 3). Upon enrolment, patients get access to the MMC. The day of the first prescription is considered T=0.

Medication Management Centre

The MMC will offer patients curated, personalised information regarding DDIs and DDGIs and a patient diary to manage and monitor their drug therapy. Additionally, the MMC will remind the patients by email to complete a questionnaire through the eClinical Data Management Platform Castor These questionnaires collect information on the experience with the MMC, clinical monitoring, clinical outcome, and adverse events, according to the schedule in table 2. Patients can report ADRs in the medication management centre through patient reported outcome measures (PROMs) in the patient diary. More information regarding the MMC can be found in section 5.1.1.

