# 3.3 Data collection procedures

T=0 is defined as the day the patient initiates the index drug (table 3). During the 12-week follow-up period, the patients will receive surveys at baseline, 2 weeks and 12 weeks and a semi-structured close-out interview at week 12. Patients are requested to complete the surveys within a week. In case a patient discontinues the index drug within the 12-week follow-up period, the follow-up will continue as initially anticipated. The questionnaires will be provided to the patients through the medication management centre.

The data collected by the surveys is summarized in table 2. The MMC will collect: 1) Data entered by patients: demographic information, medical information, symptom diary, 2) Data created by the MMC and its tools: medication plan assessed with its safety risks (DDIs, DGIs, risk score, dosing information) and 3) statistical information collected by the system about the usage of the system by individual patients, sub-cohorts and the whole cohort.

All data will be entered into an electronic Case Report Form (eCRF), which guarantees consistency of data collection procedures. Data will be used exclusively in a pseudonymous fashion and data protection will be guaranteed according to international regulations. Local, independent internal monitors will guarantee data integrity and data homogeneity across all four implementation countries by risk-based monitoring of a random sample of the collected data. The research team will collect and store patient contact information (e-mail address, telephone number, name, and study-ID number) in a separate, local file (national subject identification code list).

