#### 8. METHODS

### 8.1 Study parameters/endpoints

### 8.1.1 Main study parameter/endpoint

Proof of principle-study focused on assessing the impact of the developed MMC on patient empowerment in polypharmacy patients in order to improve drug safety. The primary endpoint is the sense of empowerment and health literacy for participants before and after use of the MMC. The endpoint consists of:

- Patient capacities, beliefs or resources including self-efficacy, sense of meaning and coherence about their condition, health literacy, perceived control and feeling respected by their healthcare providers.
- Activities or behaviours (things patient do) e.g., participate in shared decision-making by taking an active role and making informed decisions about their health and healthcare, self-manage and monitor their condition by choosing meaningful and realistic goals and taking steps to achieve those goals, participate in collective activities such as patient support or advocacy groups, and search for information about their health condition e.g., on the internet.

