### 8.2 Randomisation, blinding and treatment allocation

No randomization will be applied. The Dutch, Slovenian and Greek patients will receive the MMC with PGx testing. The German patients will get access to the MMC, but will not receive any PGx testing. We will test the user experience.

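### The primary result is an uncontrolled before/after change in HLS-EU-Q47, so the protocol cannot present it as the impact of the MMC

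*Protocol*

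**What the plan says.** Protocol section 2.1: "The primary objective is to assess the impact of the developed medication management centre on the patient empowerment of polypharmacy patients". Section 4.4 repeats the causal aim: "the sample size is aimed at showing the impact of the use of the MMC on patient empowerment and exploring associations". The same sentence adds that statistically significant relations are not the target. The section then says that no formal power calculation was done and that the results will help to design a larger study of the effect.

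Section 8.1.1: "The primary endpoint is the sense of empowerment and health literacy for participants before and after use of the MMC". The measure is the HLS-EU-Q47. An average item score of 3 or more counts as empowered, and the change in score is described as well. Table 1 marks health literacy at baseline and week 12 only.

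On comparators, section 8.2 says "No randomization will be applied", and all patients at all four sites get the MMC. Section 3.1 says the historical cohort allows an evaluation "without needing a concurrent control group". It also says that ADR prevention and the identification of drug-drug-gene interactions "will be explored as a secondary endpoint by comparing results of the pilot study with those obtained from matched historical controls".

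On timing, section 3.2: "The patient journey starts when the patient receives a first prescription for one of the index drugs". MMC access is given at enrolment. On exposure, section 3.3 says the MMC will collect "statistical information collected by the system about the usage of the system by individual patients, sub-cohorts and the whole cohort".

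**The concern.** 'Impact' is a causal word. It needs a view of what the score would have been at week 12 without the MMC, and nothing in the primary comparison supplies one.

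The protocol itself names rival explanations. Section 8.1.1 lists provider communication, access to information, a supportive care setting and education as main drivers of empowerment, and says the questionnaire covers them. Patients who have just started an index drug under regular care may well receive some of these outside the MMC.

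What is at stake is the study's only primary objective. A rise in HLS-EU-Q47 would be published as an MMC effect and carried into the planning of the larger study.

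**Working it through.** **1. Is there a comparator for the primary outcome?** There are four candidates:

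- *Concurrent or randomised group:* none (sections 3.1 and 8.2).
- *U-PGx controls:* sections 2.2, 3.1 and 8.1.2 and the Summary tie them to adverse drug events or reactions and drug-drug-gene interactions. Section 4.4 says more loosely that results will be compared with them. No section says these controls completed the HLS-EU-Q47, and matching is on age, sex and medication only.
- *German site against the others:* this contrasts pharmacogenetic testing, not the MMC, which every site receives.
- *Trend before MMC access:* Table 1 has one health literacy measurement before access and one at week 12. Section 5.1.2 lists the questionnaire loosely under weeks 2 and 12, but that adds no second measurement before access.

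MMC access and the new drug also start together. Section 3.2 sets T=0 at the first prescription and section 3.3 at the start of the index drug. On either definition the two exposures coincide.

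**2. The plan's own figure.** 4 sites x 30 = 120, which agrees. No alpha, power, SD or effect size is given, so the 30 per site cannot be rebuilt.

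**3. Effect of background drift on the share counted as empowered.** Assumptions, not from the documents: mean item score at baseline 3.2, SD 0.6, normal distribution, zero MMC effect. The cut-off of 3 is from section 8.1.1. Formula: share = Φ((mean − 3)/SD).

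| Mean at week 12 | (mean − 3)/0.6 | Share empowered | Extra patients of 120 |
|---|---|---|---|
| 3.2 (no drift) | 0.33 | 63% | – |
| 3.3 (drift 0.1) | 0.50 | 69% | about 7 |
| 3.4 (drift 0.2) | 0.67 | 75% | about 14 |

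**4. Effect of drift on the mean change.** The 95% half-width for a mean change is t(0.975, n−1)/√n in SDs of change: 0.18 for n = 120, 0.20 for 96 completers (an assumed loss of 24) and 0.37 for one site of 30. With zero MMC effect and an assumed drift, the non-central t distribution gives the probability that this interval lies wholly above zero at n = 120:

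| Assumed drift (SDs of change) | 0 | 0.1 | 0.2 | 0.3 | 0.4 | 0.5 |
|---|---|---|---|---|---|---|
| Probability | 0.025 | 0.19 | 0.58 | 0.90 | 0.99 | about 1.00 |

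At n = 96 the figures for 0.2 and 0.3 are 0.49 and 0.83. More patients raise the probability, so sample size does not cure the problem.

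**5. What logged use could add.** Assume two-sided 5% and 80% power. Splitting 120 patients 60/60 by use detects (1.96 + 0.84) x √(2/60) = 0.51 SD, with a 95% half-width of 1.96 x √(2/60) = 0.36 SD. Treating use as continuous, the detectable correlation is about 0.25. A flat gradient would therefore say little.

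**6. What a comparator would need.** With two concurrent arms of 60, power at 0.2, 0.3, 0.4 and 0.5 SD is 0.19, 0.38, 0.59 and 0.78. For 80% power, 393, 175, 99 and 63 per arm are needed. This supports leaving the effect to a larger study.

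**The case against.** The strongest reply is that this is a declared proof-of-concept study. Section 4.4 disclaims significance testing and defers formal analysis of the effect to a larger study, section 3.1 is open about having no concurrent control, and section 10 is purely descriptive. This stands against any reading that the trial sets up an invalid test. It does not rescue the word 'impact', because descriptive statistics on one group do not show it either.

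The interviews cover empowerment and impact and will be compared with the questionnaires. That is planned evidence on attribution, but it comes only from people who had the MMC.

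Three stronger readings are tempting and are not supported:

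- *That learning about the new drug will in fact inflate the scores.* This is an inference. Patients already use five or more drugs, and 31 of the 47 items (15 + 16) concern disease prevention and health promotion. If only the 16 health-care items moved, an overall drift of 0.1 to 0.2 would need 0.1 x 47/16 = 0.29 to 0.2 x 47/16 = 0.59 points on each.
- *That the use data will go unanalysed.* Neither section 8.1.1 nor section 10 relates score change to use, but section 8.6 refers to a statistical analysis plan that is not at hand and could do so. That plan could not supply a comparator, and the objective's wording is fixed in the protocol.
- *That patients who never open the MMC count the same as daily users.* Section 3.3 says the questionnaires come through the MMC, while sections 3.1 and 8.3 describe Castor with an email. By the first route, a patient with a week-12 score has opened the MMC at least once.

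**Conclusion.** The concern holds as a mismatch between claim and design. Sections 2.1 and 4.4 promise impact, the primary comparison is before/after in one group, and no element of the plan provides a counterfactual for HLS-EU-Q47. This conclusion rests on the text alone.

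The size of any background change is unknown. The figure of 7 to 14 of 120 patients depends on the assumed mean, SD and drift. It shows that a modest drift would be enough to matter, not that one will occur. The study remains useful as a descriptive pilot. What must change is what its primary result is said to show.

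**What to change.** - In sections 2.1, 4.4 and 8.1.1, word the primary result as change in HLS-EU-Q47 during 12 weeks with MMC access. State that it cannot be attributed to the MMC without a comparator, and leave the effect to the larger study that section 4.4 foresees.
- As a supportive description, show the 12-week change by the MMC use already logged per patient. Take use as a continuous measure, or in numeric categories set before the data are seen. A split at the observed median would not meet that condition. Do not count log-ins made only to complete questionnaires.
- State that use is self-selected. Do not make a gradient with use a condition for any claim or hypothesis: a positive one may reflect motivation, and a flat one is weak evidence at this size.

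The cost is wording, one extra table from data already collected, and a more modest headline claim. No new arm, visit or measurement is needed.

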### 5. TREATMENT OF SUBJECTS

#### 5.1 Investigational strategy

In this study, participants will be granted access to the MMC. This tool provides personalised patient-centred information on drug-drug interactions (DDIs) and PGx affecting polytherapy.

#### 5.1.1 The medication management centre

All patients participating in the EmPaSafe study will gain access to the Medication Management Center (MMC), a digital platform developed to empower patients with information and enhance medication safety, particularly in cases of polymedication. The MMC's primary purpose is to serve as an educational resource that provides tailored, patient-specific insights into drug-drug interactions (DDIs) and drug-drug-gene interactions (DDGIs) based on individual pharmacogenomic (PGx) profiles. These insights aim to support adherence to therapy, improve patient outcomes, and mitigate risks associated with complex medication regimens.

The MMC annotates each patient's medication plan with curated safety information sourced from validated guidelines, including those from the Dutch Pharmacogenetics Working Group (DPWG), and trusted public databases such as the ABDA-Database. By offering personalized, high-quality content, the MMC helps patients understand their therapies and the potential risks associated with their medications. It also provides tools for reporting health concerns, such as adverse drug reactions (ADRs), through integrated patient-reported outcome measures (PROMs).

A core feature of the MMC is its emphasis on patient engagement. The platform equips users with the knowledge to have meaningful discussions with healthcare providers, thereby fostering collaborative decision-making. However, the MMC strictly serves an informational purpose; it neither facilitates self-adjustment of medication nor replaces professional medical advice. This distinction ensures compliance with regulatory requirements and underscores its role as an educational rather than a diagnostic tool.

The MMC also includes advanced functionalities that may shape the future of personalized medicine. These include exploratory tools, such as machine learning models and mechanistic risk assessments, designed to analyse real-world data for predicting adverse drug reactions (ADRs). While these tools are not yet clinically validated, they represent the innovative potential of integrating cutting-edge technologies into medication management.

By enabling patients to record their experiences in health diaries and providing access to curated, reliable information, the MMC empowers individuals to actively participate in their healthcare. This approach not only improves medication safety and adherence but also aligns with the broader goals of the SafePolyMed project: enhancing the safety and effectiveness of polytherapy through patient-centred innovation.

It's important to note that all information provided by the MMC is publicly available and curated by the experts working on the SafePolyMed project. While the MMC and its tools serve to empower patients, they are not medical devices and do not replace professional medical advice or therapy adjustments. See also Appendix 2.

# 5.1.2 Questionnaires

The baseline questionnaire will comprise questions regarding demographics, in- and exclusion criteria, and comorbidities. Additionally, standardized questionnaires will be offered to the patients at 2 and 12 weeks after initiation of the index drug to obtain information about health behaviour, drug use, ADRs (PRO-CTCAE), quality of life (SF-36), MMC experience and health literacy (HLS-EU-Q47). The questionnaires are adaptive meaning that based on the provided answers only relevant follow-up questions will be asked to minimize the burden. Lastly, a semi-structured close-out interview will be held at week 12 to gather information on the experience with the MMC.

# 6. INVESTIGATIONAL PRODUCT

Not applicable

**6.1 Name and description of investigational product(s)** Not applicable

**6.2 Summary of findings from non-clinical studies** Not applicable

**6.3 Summary of findings from clinical studies** Not applicable

6.4 Summary of known and potential risks and benefits Not applicable

6.5 Description and justification of route of administration and dosage Not applicable

**6.6 Dosages, dosage modifications and method of administration** Not applicable

6.7 Preparation and labelling of Investigational Medicinal Product Not applicable

6.8 Drug accountability Not applicable

## 7. NON-INVESTIGATIONAL PRODUCT

#### 7.1 Name and description of non-investigational product(s)

Not applicable.

**7.2 Summary of findings from non-clinical studies** Not applicable.

**7.3 Summary of findings from clinical studies** Not applicable.

**7.4 Summary of known and potential risks and benefits** Not applicable.

**7.5 Description and justification of route of administration and dosage** Not applicable.

**7.6** Dosages, dosage modifications and method of administration Not applicable.

**7.7 Preparation and labelling of Non-Investigational Medicinal Product** Not applicable.

**7.8 Drug accountability** Not applicable.

#### 8. METHODS

### 8.1 Study parameters/endpoints

### 8.1.1 Main study parameter/endpoint

Proof of principle-study focused on assessing the impact of the developed MMC on patient empowerment in polypharmacy patients in order to improve drug safety. The primary endpoint is the sense of empowerment and health literacy for participants before and after use of the MMC. The endpoint consists of:

- Patient capacities, beliefs or resources including self-efficacy, sense of meaning and coherence about their condition, health literacy, perceived control and feeling respected by their healthcare providers.
- Activities or behaviours (things patient do) e.g., participate in shared decision-making by taking an active role and making informed decisions about their health and healthcare, self-manage and monitor their condition by choosing meaningful and realistic goals and taking steps to achieve those goals, participate in collective activities such as patient support or advocacy groups, and search for information about their health condition e.g., on the internet.

Literature shows that effective patient-provider communication, access to health information, a supportive healthcare environment and educational interventions can be listed as the main drivers for patient empowerment.(7-10) The health literacy questionnaire (HLS-EU-Q47) includes questions regarding these main drivers, but also the mentioned capacities, beliefs and resources, as well as activities or behaviour regarding patient empowerment. Health literacy can therefore be used as a proxy for patient empowerment.(11; 12) The questionnaire is validated in all four local languages (Dutch, German, Greek and Slovenian). The questionnaire is divided into three domains: health care (16 questions), disease prevention (15 questions) and health promotion (16 questions). These domains are subdivided into 4 categories: Accessing information, Understanding information, Appraising information and Applying information. Together, these domains cover 47 questions. The scores for the domains will be calculated using the instrument's scoring rules. For the questions incorporated in the questionnaire. Each question will have 5 responses: 1 = Cannot do or always difficult, 2 = Usually difficult, 3 = Sometimes difficult, 4 = Usually easy and 5 = Always easy.(11) A cut off of  $\geq$ 3 was determined to quantify empowerment because scores of 1 to 3 on each item indicate a level of difficulty ('cannot do or always difficult', 'usually difficult' or 'sometimes difficult'). Descriptive statistics will be performed to analyse the results. An average score of  $\geq 3$  is defined as 'empowered' and serves as endpoint. Secondary, the growth in empowerment will be guantified, specifying the change in scores. The overall score will be evaluated to assess whether the endpoint has been achieved, and the analysis will take into account both proportions and the magnitude of growth in empowerment.

A semi-structured close-out interview to obtain information on the patient experience of the medication management centre will be held. This interview can be divided into six sections: General experience with the MMC, Usability of the MMC, Patient empowerment, Impact, App features and functionality and Suggestions for improvement. All sections contain two to three questions each. This semi-structured close-out interview should be performable within an hour.

The interviews will be performed on a random sampling basis, until the saturation point is reached. This method allows for the collection of sufficient, diverse insights while minimizing redundancy.(13; 14) The interviews will be recorded using voice recorders and transcribed using ATLAS.ti to be able to analyse the responses.

The responses will then be categorized using a framework-analysis to capture higher-order concepts (e.g. "more involved in decisions" and "understood medication better" may form the category 'Empowerment' while "easy to navigate" and "intuitive layout" may form the category 'Usability Strengths'). After that, we will develop overarching themes based on these categories (e.g. "The MMC improves patient empowerment through enhanced medication understanding"). The analysis will be performed according to AMEE-guide No. 164. The analysis will start deductively, using the existing framework, while allowing space for inductive insights to emerge, such as new themes or patterns that arise from the data.(15) Analysis of the responses will be performed within ATLAS.ti, To ensure accurate and consistent coding, we will implement agreement sessions where team members will collaboratively review and align their coding approaches. The findings from these interviews will be compared to questionnaire results to identify convergence or divergence.

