**Intervention**: The MMC that provides patient centred information on drug-drug interactions and pharmacogenetics affecting personal polytherapy. The MMC will show a selection of high quality publicly available information such as details on different types of medications, including their uses, side effects and instructions for use, in the language of the patient. This information is targeted at an individual patient's medication profile to inform patients to better understand and deal with their personal health information, with regard to drug therapy. Patients in the Netherlands, Slovenia and Greece also will receive their PGx profile to further personalise the MMC experience.

**Main study parameters/endpoints**: The primary outcome is the sense of empowerment and health literacy for participants before and after use of the MMC. Secondary outcomes include an evaluation of the drug-drug-gene interactions and adverse drug events in the study populations compared to matched historical controls.

Nature and extent of the burden and risks associated with participation, benefit, and group relatedness: Patients are exposed to the regular treatment. In addition, patients will receive questionnaires at baseline, two, and twelve weeks regarding the use and experience of the medication management centre, and a close-out interview at week twelve. In addition, 10ml of blood will be collected during a venipuncture for pharmacogenetic analyses.

Benefits include having access to the medication management centre for the duration of the study. Additionally, patients will receive their PGx profile. This can be used to individualize drug treatment, based on the Dutch Pharmacogenetics Working Group (DPWG) guidelines.

Overall, minimal risks are expected for subjects as they will receive normal clinical care. Information from the MMC will be a curation of existing publicly available data. Any information regarding DDIs and DGIs will be supplemented with a disclaimer that the patient should not adjust their treatment without talking to a healthcare provider.

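### The primary endpoint counts an average score of 3 or more as 'empowered', but the protocol's stated reason places a score of 3 in the difficulty range

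*Protocol*

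**What the plan says.** Protocol section 8.1.1 uses the HLS-EU-Q47 as a proxy for patient empowerment. The questionnaire has 47 items in three domains (16, 15 and 16), each answered from 1 to 5. The three lowest labels all describe difficulty, and the upper part of the scale reads "3 = Sometimes difficult, 4 = Usually easy and 5 = Always easy".

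The section sets a cut-off of ≥3, which it says was "determined to quantify empowerment because scores of 1 to 3 on each item indicate a level of difficulty". The next step classes an average of ≥3 as 'empowered'. That status is what the text says stands "and serves as endpoint. Secondary, the growth in empowerment will be" quantified. On how the result will be judged, it adds that "the analysis will take into account both proportions and the magnitude of growth in empowerment".

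The same section opens with the statement that "The primary endpoint is the sense of empowerment and health literacy for participants before and after use of the MMC", and the Summary says the same. Section 10.1 adds only that the primary outcome will be described with descriptive statistics.

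**The concern.** The protocol states a rule and a reason for it, and they disagree about the score of 3. If item scores of 1 to 3 show difficulty, a threshold built on that reason should leave 3 out. The rule lets 3 in.

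The primary result of this study will be a description, and part of it is the proportion of patients who carry the label 'empowered'. A reader who takes the label from the stated reason would think these patients had, on average, moved out of the difficulty range. Under the rule as written, a patient can carry the label without a single answer on the easy side of the scale.

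**Working it through.** **Inputs, all from protocol section 8.1.1**
- Items: 16 + 15 + 16 = 47, which agrees with the stated total.
- Scale: 1 to 5, with 1, 2 and 3 labelled as degrees of difficulty and 4 and 5 as degrees of ease.
- Rule: average ≥3 means empowered.
- Reason: item scores of 1 to 3 mean difficulty.

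The protocol has no sample size or power figure that depends on the cut-off, so there is none to reproduce. I take the average as the plain mean of all 47 items on the 1 to 5 scale, with every item answered.

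**Step 1: rule and reason at the boundary**

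| Score | Under the stated reason | Under the rule |
|---|---|---|
| 3 | difficulty | empowered |

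The conflict is direct. It cannot easily be put down to one mistyped sign, because ≥3 appears once where the cut-off is introduced and again where 'empowered' is defined.

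**Step 2: what the rule admits**

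The total needed for an average of 3 is 47 × 3 = 141.
- All 47 items at 3: 141/47 = 3.00. The patient passes with no answer of 4 or 5.
- 45 items at 3, one at 2 and one at 4: (135 + 2 + 4)/47 = 141/47 = 3.00. The patient passes with 46 of 47 answers in the difficulty range.

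The first case does not depend on how the average is formed. If it were taken by domain, all answers at 3 would give 48/16 = 3.00 and 45/15 = 3.00.

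**Step 3: what changing ≥ to > achieves**

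Totals are whole numbers, so >3 means a total of at least 142. With complete answers, only patients with a total of exactly 141 change class.
- 46 items at 3 and one at 4: (138 + 4)/47 = 142/47 = 3.02. This patient still passes.

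The change removes the literal contradiction. It does not ensure that a patient called empowered finds most tasks easy, because the reason is about single items and the rule is about an average.

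**Step 4: does another section repair it?**

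The general definition at the start of section 8.1.1 gives no threshold, and section 10.1 gives no analysis detail beyond descriptive statistics. Section 8.1.1 does say that "The scores for the domains will be calculated using the instrument's scoring rules", but that sentence concerns domain scores. The cut-off rests on its own reason from the item labels.

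**The case against.** The strongest reply is that this is a proof-of-concept study with no formal sample size calculation (section 4.4) and a descriptive analysis (section 10.1). No test, error rate or sample size depends on the cut-off. The change in scores is planned and does not use it, and the interview findings will be compared with the questionnaire results. All of this stands and limits the consequence. It does not reconcile the rule with its reason.

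A second reply is that a statistical analysis plan, which section 8.6 foresees, could settle the matter. It could settle how results are tabulated. The contradiction, however, lies in the protocol's definition of its primary endpoint. A plan that changed the cut-off would depart from the protocol, and one that kept it would carry the contradiction forward.

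Two stronger readings are tempting, and the documents support neither.

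- **Status at week 12 only.** A reader might infer that the endpoint ignores where patients started, because the ≥3 status has no visit attached and the change in scores is called secondary. But the Summary states that "The primary outcome is the sense of empowerment and health literacy for participants before and after use of the MMC", and section 8.1.1 repeats it. Table 1 in section 3.1 schedules health literacy at baseline and at 12 weeks, and both proportions and growth are planned. This also fits the objective in section 2.1, which is about the impact of the medication management centre. The visit at which status is tabulated is detail that an analysis plan commonly settles.
- **Averages just above 3.** A reader might infer that the protocol's labels also make every average slightly above 3 a state of difficulty. They do not, because the stated reason covers item scores of 1 to 3. The 3.02 example shows that a bare >3 needs its own justification. It does not show a second contradiction.

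**Conclusion.** The cut-off in section 8.1.1 is wrong as written: it contradicts the only reason the protocol gives for it, and nothing else in the document resolves this. The boundary case is exact and needs no assumption about the data: 'sometimes difficult' on all 47 items gives 141/47 = 3.00 and is classed as empowered.

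The consequence is confined to the label. Under a threshold that excludes 3, the percentage called empowered can only stay the same or fall. How far it would fall cannot be computed, because the protocol gives no baseline scores and no expected distribution. The averages shown assume complete answers on the 1 to 5 scale. The before-and-after framing of the endpoint is adequate and is not part of the error.

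This should be corrected, and confidence in the contradiction is high.

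**What to change.** Before data are seen, replace ≥3 in both sentences of section 8.1.1 with a threshold that excludes 3. The minimum change consistent with the stated reason is an average >3. Because that still admits an average of 3.02 with one easy answer, the sponsor should state why the chosen value is right for an average, arguing from the item labels or from the instrument's scoring rules that the section already invokes. Keeping 3 and writing a new reason would be weaker, because 'sometimes difficult' throughout would still count as empowered.

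In the same edit, one sentence can say that the proportion above the cut-off is described at baseline and at week 12. This is a clarification in line with the existing definition, not the repair of a separate error.

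No new data are needed, since health literacy is already collected at both visits. The cost is a protocol amendment. If it is substantial, section 12.3 requires notice to the ethics committee and the competent authority, and section 11.2 requires the national principal investigators to obtain written ethical approval or a favourable opinion. The percentage called empowered may also be lower than under the present rule.
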